7.10. Modified Allen Test

The Modified Allen Test will be performed at screening for Part 0 and Part A subjects only.

A modified Allen test measures arterial competency, and should be performed for both hands. The procedure for performing the test is as follows (derived from

1. The subject is instructed to clench his fist; if the subject is unable to do this, the subject's hand is to be tightly closed by the assessor.
2. Using fingers, occlusive pressure is applied to both the ulnar and radial arteries, to obstruct blood flow to the hand.
3. While applying occlusive pressure to both arteries, the subject should relax his hand, and a check is performed as to whether the palm and fingers have blanched, to ensure that the arteries are completely occluded.
4. The occlusive pressure on the ulnar artery is released to determine whether the modified Allen test is positive or negative:
 - Positive modified Allen test – If the hand flushes within 5 to 15 seconds it indicates that the ulnar artery has good blood flow; this normal flushing of the hand is considered to be a positive test.
 - Negative modified Allen test – If the hand does not flush within 5 to 15 seconds, it indicates that ulnar circulation is inadequate or nonexistent.

7.11. Columbia Suicide Severity Rating Scale

The C-SSRS (screening version) will be used at screening to rate the subject's degree of suicidal ideation on a scale ranging from "no suicidal ideation" to "active suicidal ideation with specific plan and intent" (Posner et al 2011). Subjects with a history of suicidality based upon clinical history or C-SSRS scoring will not be eligible for the study. The person administering the C-SSRS should have performed the rater training and have obtained a training certificate within the previous 2 years.

In any event of suspected active suicidality (eg, active suicidal ideation or intent, significant suicidal behavior) or clinical findings suggesting that the subject is dangerous to himself or herself, the subject should be referred for immediate psychiatric evaluation.

The version of C-SSRS used will be translated into German and linguistically validated.

7.12. Unified Huntington's Disease Rating Scale Total Motor Score (UHDRS-TMS) (HD Patients Only)

For HD patients only, UHDRS-TMS is performed at the time points detailed in [Table 1](#).

The UHDRS comprises a broad assessment of features associated with HD. It is a research tool which has been developed to provide a uniform assessment of the clinical features and course of HD.

The TMS component of UHDRS comprises 31 assessments from the 15 items of the UHDRS, with each assessment rated on a 5-point scale from 0 (normal) to 4 (maximally abnormal).

7.13. Methods and Time Points of Assessing, Recording, and Analyzing Safety Data

All adverse events will be reviewed on a periodic basis by the CPP/medical monitor according to the safety monitoring plan (eg, scheduled safety reviews for pridopidine) as interim/preliminary safety databases become available. In addition, safety data will be evaluated periodically and ad hoc (if necessary) in the Product Safety Group.

Methods and time points of assessing safety data are discussed in [Section 3.14](#). Procedures for recording safety data are discussed in [Section 13.1](#) and methods of analyses are discussed in [Section 9.10.2](#).

8. ASSESSMENT OF BIOMARKERS AND PHARMACOGENETICS

8.1. Assessment of Exploratory Biomarkers

8.1.1. Biomarker Assessments

Biomarkers are defined as biological substances that monitor physiological effects, assessing drug activity, predicting clinical outcome, safety, and treatment response.

Biomarker assessment potentially includes the following:

[REDACTED]

[REDACTED]

[REDACTED]

[REDACTED]

The final list of biomarkers that will be investigated will be selected at a later stage before the analysis so as to allow updating with new scientific information.

8.1.2. Pharmacogenetic Assessment

[REDACTED] and it is known that subjects with functional mutations resulting in inactive enzyme will show higher exposures and are at greater risk of known emergent adverse events. As a result, DNA will be collected, and subjects identified as poor CYP2D6 metabolizers will be excluded from the study. Remnant DNA will also be genotyped to identify extensive, intermediate and ultra CYP2D6 metabolizers. Genotyping may also be conducted for QTc in the event of any emergent safety findings. In addition, functional genetic polymorphisms have been described in the S1R receptor that results in decreased receptor expression (Miyatake et al 2004). Examination of the known S1R polymorphisms did not impact fluvoxamine displacement with SA4503 (Ishikawa et al 2007). However, the impact of these polymorphisms on fluspidine displacement is not known.

[REDACTED]

[REDACTED]

Genetic long QT syndrome genotyping may also be conducted retrospectively and assessed only in subjects experiencing QT prolongation following study drug administration leading to study discontinuation. Blood sampling for pharmacogenetics can be performed at a separate visit within the screening period after informed consent is obtained.

8.1.3. Specimen Sampling and Handling

8.1.3.1. Biomarker Samples

For all dose cohorts ≥ 2.5 mg, biomarker blood samples of 4 mL to provide 2 mL serum, 4 mL to provide 2 mL plasma, with an additional 2.5 mL collected in a PAXgene tube will be collected. For the 0.5 and 1 mg dose cohort in Part A, biomarker blood samples of 2 mL for plasma, 2.5 mL of PAXgene tube, and no serum samples will be collected.

The date and time of each biomarker sample and the dates and times of the last drug administration prior to any collected biomarker sample will be recorded on the source documentation and transcribed onto the CRF. Only major deviations ($>5\%$) from the scheduled blood sampling time points will be commented on the respective page of the CRF.

When the biomarker blood sample collection coincides with pharmacokinetic measures, the biomarker samples should be collected after pharmacokinetic sampling.

For plasma, samples will be collected in lavender-top (K₃EDTA) Vacutainer venous blood collection tubes following site standard phlebotomy practices and procedures. Immediately following collection, the tube should be gently inverted 4 to 8 times, and cooled on wet ice. Within 45 minutes of collection, the tube should be centrifuged at approximately 4°C at 1500 \times g for 15 minutes. The plasma should then be immediately transferred into 2 polypropylene tubes (first aliquot [Set A] and back-up [Set B]) and stored below -70°C (or -20°C in a non-defrosting freezer if -70°C is not available) until shipment to the sponsor specified biorepository [REDACTED], where they will be retained for at least 15 years.

For serum, samples will be collected into red-top Vacutainer tubes (serum separators should not be used) following site standard phlebotomy practices and procedures. Tubes should be gently inverted 4 to 6 times and stored upright at room temperature for 30 to 45 minutes. Within 45 minutes of collection, tubes should be centrifuged at approximately 4°C at 1500 \times g for 15 minutes. The serum should then be immediately transferred into 2 polypropylene tubes (first aliquot [Set A] and back-up [Set B]) and stored below -70°C (or -20°C in a non-defrosting freezer if -70°C is not available) until shipment to the sponsor specified biorepository [REDACTED], where they will be retained for at least 15 years.

For RNA, samples will be collected into a PAXgene blood RNA tube at room temperature following site standard phlebotomy practices and procedures. The PAXgene tube should be collected after the serum and plasma collections and held in an upright vertical position below the donor's arm during blood collection. For a complete blood draw, at least 10 seconds should be allowed and it should be ensured that blood has stopped flowing into the tube before

removing from the holder. The PAXgene blood RNA tube should be gently inverted (not shaken) 8 to 10 times and stored upright at room temperature. The tube should be incubated at room temperature for 2 hours to ensure complete lysis before freezing. Samples should be frozen for at least 24 hours at -20°C and then transferred to -70°C until shipment to the sponsor specified biorepository [REDACTED], where they will be retained for at least 15 years.

8.1.3.2. Pharmacogenetic Samples

Pharmacogenetic blood samples will be collected at screening only. For all dose cohorts ≥ 2.5 mg, the pharmacogenetic blood should be collected into a 4.9-mL (K₃EDTA) Sarstedt Monovette® venous blood collection tube labeled with the subject coded number and following site standard phlebotomy practices and procedures. For the 0.5 and 1 mg dose cohort in Part A, the pharmacogenetic blood should be collected into a 2.7-mL (K₃EDTA) Sarstedt Monovette® venous blood collection tube labeled with the subject coded number and following site standard phlebotomy practices and procedures.

Immediately following collection, the tube should be gently inverted (not shaken) 4 to 8 times. The tubes must not be centrifuged. Samples are to be stored and shipped at 4°C if they are to arrive to the genotyping laboratory within 48 hours for CYP2D6 genotyping; if not, samples should be stored at -20°C in a non-defrosting freezer at the study site until shipment [REDACTED]
[REDACTED]
[REDACTED]

8.1.4. Shipment and Analysis of Samples

8.1.4.1. Biomarker Samples

Biomarker sample aliquots should be shipped on dry ice by overnight courier to [REDACTED]
[REDACTED] and stored at -70°C. Vendor contact details will be provided by the sponsor.

8.1.4.2. Pharmacogenetic Samples

Pharmacogenetic samples should be shipped by overnight courier to a specified vendor [REDACTED]
[REDACTED] during screening (either ambient if to be received by the genotyping laboratory within 48 hours or on dry ice if stored at -20°C). Remnant DNA should be retained and stored at the vendor until the end of study and then shipped to the biorepository [REDACTED]
[REDACTED] The remnant samples will be labeled with a new code so genetic data will not be recorded with a subject number.

9. STATISTICS

This section describes the statistical analysis as foreseen at the time of planning the study. Changes, additions, and further details about the analyses will be described in the statistical analysis plan. After finalization of the statistical analysis plan, any additional analyses or changes to analyses that may be required will be fully disclosed in the clinical study report (CSR).

9.1. Sample Size and Power Considerations

This PET study is exploratory in nature; therefore, no formal hypothesis testing is planned. Thus, based on clinical and practical considerations, a sample size of up to approximately 38 subjects (up to 4 subjects per dose level) is considered adequate for this type of study and to attain the study objectives. Up to 45 subjects are planned to be enrolled in this study to ensure up to 38 evaluable subjects. Adaptive study design will allow increasing or reducing the study total sample size or each dose/time cohort as necessary. This sample size may include up to 4 patients with HD, which may be added to study engagement of pridopidine to the D2R and to explore the effects of neurodegeneration.

It is anticipated that 3 dose levels will be sufficient to characterize the exposure-response profile. However, additional cohorts may be studied.

9.2. Analysis Sets

9.2.1. Enrolled Analysis Set

The enrolled analysis set will include all enrolled subjects, regardless of whether or not a subject took any study drug. A subject is considered enrolled according to the status reported in the database.

9.2.2. Safety Analysis Set

The safety analysis set will include all subjects who receive at least 1 dose of study drug. In this analysis set, treatment will be assigned based on the treatment subjects actually received.

9.2.3. Pharmacokinetic Analysis Set

The pharmacokinetic analysis set will include those subjects in the safety analysis set who have sufficient data to calculate at least 1 evaluable pharmacokinetic parameter for pridopidine or its metabolites.

9.2.4. Pharmacodynamic Analysis Set

The pharmacodynamic analysis set will include those subjects in the safety analysis set who have evaluable imaging data before and after pridopidine administration.

9.3. Data Handling Conventions

For all variables, only the observed data from the subjects will be used in the statistical analyses, ie, there is no plan to estimate missing data, unless otherwise specified. Detailed data imputation rules will be described in statistical analysis plan.

9.3.1. Handling Withdrawals and Missing Data

Missing data will not be imputed, unless otherwise specified.

9.4. Study Population

The enrolled analysis set (see Section 9.2) will be used for all study population summaries unless otherwise specified.

9.4.1. Subject Disposition

Data from subjects screened, subjects screened but not enrolled (and reason not enrolled), subjects who are enrolled, subjects enrolled but not treated (and reason), subjects in the safety and pharmacokinetic analysis sets, subjects who complete the study, and subjects who withdraw from the study will be summarized using descriptive statistics. Data from subjects who withdraw from the study will also be summarized by reason for withdrawal using descriptive statistics.

9.4.2. Demographic and Baseline Characteristics

Subject demographic and baseline characteristics, including medical history, prior medications, and ECG findings, will be summarized using descriptive statistics. For continuous variables, descriptive statistics (number [n], mean, standard deviation [SD], median, minimum, and maximum) will be provided. For categorical variables, subject counts and percentages will be provided. Categories for missing data will be presented if necessary.

9.5. Pharmacodynamic Analysis

9.5.1. Analysis with (S)-(-)-[¹⁸F]fluspidine

Details of the analysis to be performed are presented in Section 6.2.1.1.

The occupancy data for the study will be combined with the plasma concentration of pridopidine and used to derive the in vivo affinity of pridopidine for the S1R and the time-course of the occupancy of S1R by pridopidine.

Test-retest variability of (S)-(-)-[¹⁸F]fluspidine uptake will be estimated using 2 baseline (S)-(-)-[¹⁸F]fluspidine scans in up to 6 subjects. This will be used to calculate the uncertainty of the RO estimate.

9.5.2. Analysis Using [¹⁸F]fallypride

The analysis using [¹⁸F]fallypride will be similar to that using (S)-(-)-[¹⁸F]fluspidine.

For calculation of BP_{ND} and RO for [¹⁸F]fallypride, a tissue reference model can be used using the cerebellum as reference region without specific binding.

9.6. Pharmacokinetic Analysis

The pharmacokinetic parameters to be calculated for pridopidine and its metabolite TV-45065 in the plasma using non-compartmental methods, when possible, are detailed in Section 6.1.

Additional pharmacokinetic parameters, including partial AUCs and corresponding C_{average} to be inclusive of the PET scan duration, may be calculated as well, as deemed necessary.

No formal statistical analyses of the pharmacokinetic data will be performed. All data will be listed and summarized descriptively by cohort (dose) and status (healthy subject or HD patient) and presented in tabular and graphical form where appropriate. The pharmacokinetic analysis set (see Section 9.2.3) will be used for all pharmacokinetic analyses.

9.7. Pharmacokinetic/Pharmacodynamic Analysis

The relationship between the pridopidine plasma concentrations and the RO will be explored graphically. If possible, an exposure-response model will be developed to quantitatively define the relationship between RO and pridopidine exposure. It will be based on the following E_{max} model (equation) to fit the pharmacokinetic-pharmacodynamic (PK/PD) data (Grachev et al 2014):

$$E = \frac{E_{\text{max}} \times C}{EC_{50} + C}$$

Where E represents the receptor occupancy (%); C is the plasma concentration (ng/mL) corresponding to the receptor occupancy E; E_{max} is an asymptote representing the maximum receptor occupancy (%); EC_{50} is the plasma concentration (ng/mL) corresponding to 50% of E_{max} .

Two additional parameters derived to characterize various levels of receptor occupancy are:

- EC_{80} - the plasma concentration (ng/mL) corresponding to 80% of E_{max} . It is calculated directly from the equation by substituting $E=80\%$ of E_{max} and then solving for C.
- EC_{opt} - plasma concentration (ng/mL) corresponding to optimal receptor occupancy. EC_{opt} was defined as the lowest observed plasma concentration that achieved the model estimated E_{max} .

Details of the analysis will be provided in a separate analysis plan.

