2.5. Sequence of Planned Analyses

2.5.1. Planned Interim Analyses

There will be no formal interim analysis for this study. PET data will be analyzed after each cohort for selection of the next cohort dose.

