11. PHARMACOKINETIC/PHARMACODYNAMIC ANALYSIS

The pharmacokinetic/pharmacodynamic analyses will be performed outside of the scope of this SAP. The pharmacokinetic/pharmacodynamic results will be analyzed and reported separately.

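### EC_opt is the lowest observed concentration reaching the fitted Emax, but Emax is an asymptote, so EC_opt is either undefined or set by residual error

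*Protocol*

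**What the plan says.** Protocol 9.7 states that, if possible, "an exposure-response model will be developed to quantitatively define the relationship between RO and pridopidine exposure". The model is E = Emax × C/(EC50 + C), and Emax "is an asymptote representing the maximum receptor occupancy". The section then adds: "Two additional parameters derived to characterize various levels of receptor occupancy are" EC80 and EC_opt.

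- **EC80** is the concentration at 80% of Emax. "It is calculated directly from the equation by substituting" that value and solving for C.
- **EC_opt** is described as the "plasma concentration (ng/mL) corresponding to optimal receptor occupancy". It "was defined as the lowest observed plasma concentration that achieved the model estimated" Emax.

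The synopsis carries the same definitions. Protocol 9.7 leaves further detail to a separate analysis plan, and SAP section 11 says: "The pharmacokinetic/pharmacodynamic analyses will be performed outside of the scope of this SAP". Nothing in either document gives a tolerance around Emax, a fraction of Emax, or a rule for the case where no observation qualifies.

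**The concern.** The two definitions are built differently. EC80 is solved from the fitted curve. EC_opt asks for an observed point that reaches a value the curve only approaches as concentration goes to infinity. Both readings of the rule fail:

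- **Judged on the fitted curve**, no concentration qualifies.
- **Judged on observed occupancies**, a point qualifies only because it lies far enough above the curve. Its excess is residual error, including error in the fitted Emax itself.

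The concentration–occupancy relationship for S1R is a primary objective (Protocol 2.2.1). EC_opt is one of only two parameters reported beyond Emax and EC50, and it is the one labelled optimal, so readers are likely to quote it. Poorer PET precision makes it more likely to exist and tends to make it lower. Imprecise data would then appear to support a lower concentration as optimal.

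**Working it through.** **Algebra (no assumptions beyond the protocol's equation).** Setting E = f × Emax gives C = EC50 × f/(1 − f).

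- f = 0.80: 0.80/0.20 = 4, so C = 4 × EC50. This is the protocol's EC80.
- f = 0.90: 9 × EC50. f = 0.95: 19 × EC50. f = 0.99: 99 × EC50.
- f = 1: the denominator is zero, so no finite C exists.

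The distance from curve to asymptote is Emax − E(C) = Emax/(1 + C/EC50), which is positive for every finite C. An observed occupancy reaches the fitted Emax only if its residual is at least this large. With Emax assumed to be 95%:

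- C = 4.5 × EC50: 95/5.5 = 17.3 points
- C = 25 × EC50: 95/26 = 3.7 points
- C = 90 × EC50: 95/91 = 1.0 point

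**Simulation inputs.** From the documents: the model, up to 4 subjects per dose level, and 3 dose levels anticipated with more possible (Protocol 9.1). Assumed, because the documents give no values: true Emax 95%; log-normal concentrations with 30% CV around each nominal level; additive normal occupancy error with SD 3, 5 or 8 points. Each scenario had 4,000 trials with a least-squares Emax fit. EC_opt was taken as the lowest concentration whose observed occupancy was at or above the fitted Emax.

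| Levels (× EC50) | EC_opt undefined, SD 3 / 5 / 8 | Median EC_opt where defined (× EC50) |
|---|---|---|
| 1, 5, 25 | 65% / 32% / 14% | 29 / 26 / 23 |
| 1, 10, 90 | 10% / 3% / 1% | 84 / 76 / 53 |
| 0.5, 1, 5, 22.5, 90 | 7% / 1% / 0.1% | 70 / 30 / 22 |
| 1, 4.5, 18 | 83% / 53% / 24% | not tabulated |
| 0.25, 1.1, 4.5 | 100% / 99.5% / 93% | not tabulated |

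With no error, EC_opt is undefined in every trial of every layout, as the algebra requires.

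**Spread.** With five levels and SD 5, the 5–95% range of EC_opt is 15.5 to 107 × EC50, and 107/15.5 is about 7-fold. Model occupancy at those ends is 15.5/16.5 = 94% and 107/108 = 99% of Emax. In the same trials, 9 × fitted EC50 ranges from 7.7 to 10.3 × EC50.

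**Dependence on sample size.** A separate simulation used 1, 5, 22.5, 45 and 90 mg, with concentration proportional to dose, EC50 at the 2 mg concentration and SD 5. Median EC_opt fell from 30 to 24, 18, 14 and 11 × EC50 as subjects per dose rose from 2 to 4, 8, 16 and 50. A larger study gives a lower answer, so the rule does not estimate a fixed quantity.

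**The case against.** **Reach.** The study is exploratory, with no hypothesis test, and the model is fitted only if possible. Emax, EC50, EC80, the fitted curve and individual occupancies are untouched. Dose selection rests on occupancy results and time-activity profiles (Protocol 3.1); the SAP says "PET data will be analyzed after each cohort for selection of the next cohort dose" and does not mention EC_opt. This stands and limits the damage to one descriptive parameter.

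**The separate plan may repair it.** It might contain a tolerance or a not-estimable rule, and it was not available here. But the definition itself is already fixed in the protocol. A plan that follows it inherits the defect, and one that repairs it departs from the protocol.

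**Error is not the only driver.** EC_opt also depends on which concentrations are studied. In the 1, 5, 25 layout, raising SD from 3 to 8 moves the median only from 29 to 23 × EC50, within the 30% CV of the top cohort. This is fair, and it gives a second reason why EC_opt is not a property of the drug.

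**Additive error may be the wrong model.** Occupancy is one minus a ratio of binding potentials, so its error may shrink as occupancy rises. With an assumed error SD of 10, 15 or 20% of (100 − RO), EC_opt is undefined in:

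- 98%, 89% and 82% of trials (levels 1, 5, 25)
- 74%, 55% and 48% (levels 1, 10, 90)
- 73%, 54% and 41% (five levels, where the medians are 97, 86 and 78 × EC50)

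The percentages above are therefore illustrations. The definition fares no better: EC_opt is undefined more often, and it still falls as error grows.

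**The comparison with EC90 is uneven.** EC90 is EC50 rescaled, so its narrow range is only the precision of EC50. That is correct. The comparison shows that a curve-based quantity is estimable, not that EC90 carries new information.

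**Conclusion.** The concern holds: the definition is wrong as written. That EC_opt cannot exist on the fitted curve, and exists on observed data only through a positive residual, follows from the protocol's own equation and needs no assumed values. How often it is undefined, and how far it falls with noise, depends on the assumed EC50, error model and dose layout. Under additive error the undefined share ran from 0.1% to 100% across the scenarios examined. It should be fixed, because a parameter labelled optimal should not move down as measurement gets worse, but the consequences stop at this one reported number.

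**What to change.** In Protocol 9.7, the synopsis and the PK/PD analysis plan, replace the EC_opt rule with a concentration solved from the fitted equation at a fraction of Emax stated in advance. For example: EC90 = 9 × EC50, reported with a confidence interval from the fit and flagged as extrapolated when it exceeds the highest observed concentration. Keep EC80 = 4 × EC50 and drop the label optimal. Settle the fraction before the model is fitted, since moving from 90% to 99% of Emax changes the answer 11-fold (99/9).

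A tolerance applied to observed points would make EC_opt exist more often but would leave it dependent on residuals. Deleting EC_opt would also remove the defect.

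The cost is one sentence in each document and no data. Protocol 11.1.1 may require a formal amendment. If none is otherwise planned, the corrected definition can go in the PK/PD plan, with the departure disclosed in the study report.

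There are two drawbacks. EC90 is a fixed multiple of EC50, so it helps readability rather than adding information. And if the highest level is only about 4.5 × EC50, EC90 lies beyond the highest observed concentration in 88% to 95% of simulated trials (SD 8 to 3), which is why the flag is needed.
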